The PROMIS Upper Extremity Score has convergent validity with other tests used in the assessment of arm function in children with congenital limb abnormalities¹⁴, as well as with physiological tests of upper limb function (Grip Strength and Pinch Strength r>0.6 p<0.05). In the congenital limb population the PROMIS test was also the only tool without ceiling effects (when using the computer adaptive test but not a short form). The PROMIS Upper Extremity Score for Children appears to be the best tool to assess functional recovery in this group of patients. There is now agreement from an international group planning multicentre paediatric orthopaedic trials (IMPACCT), that the PROMIS Upper Extremity Tool is the preferred outcome to assess upper limb function in children. Within the SCIENCE trial, the lowest age of participating children is 7-years old. We are aware that self-reported PROMIS measures are generally used from 8-years-old, however outcome experts, including the developers of PROMIS, have advised us to use a single version of the questionnaire. Given this, we will collect self-reported function amongst all age children within the trial.

The secondary outcome measures in this trial are:

Sports/ Performing Arts Module of DASH¹⁵. This is a tool for recording details of sports and performing arts participation relating to upper extremity function. Clinicians and children have both indicated that sports participation must be considered within the analysis. DASH S/PA Module, is distinct from the more general DASH tool that lacks face validity amongst children. Although the DASH S/PA Module was not specifically developed in children, we have worked with our group of patient representatives to ensure that the tool is appropriate for use in children. There was universal agreement amongst patients (i.e. those present at an 'Elbow Study Day' that we held at Chester Zoo

in England and members of the NIHR Young Persons Advisory Group) that DASH S/PA Module has appropriate language to be used amongst children who are able to comprehend other self-reported questionnaires. The DASH S/PA Module therefore has face validity amongst the target population.

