7.2 Sample size

The primary outcome is the PROMIS Upper Extremity Score for Children. Raw scores are translated into standardised T-scores with a population mean of 50 and a Standard Deviation (SD) of 10. The 'Minimally Clinically Important Difference' (MCID) for the PROMIS Upper Extremity Score amongst children with milder forms of disability has been demonstrated to be three to four²⁵. In general, the bank of paediatric PROMIS measures have an MCID of three points, in a range of different diseases including sickle/asthma/nephrotic syndrome/cancer²⁶. During a patient and public involvement event, it was established that whilst a score of 3-4 points appeared to be the minimal difference noticeable to parents, the clinically important difference required to justify surgery was 5 points or more. Parents and children demanded a larger effect size to justify the intervention of surgery. Other studies have similarly highlighted that patients often seek greater effect sizes to warrant surgical interventions than the established MCID²⁷. We seek to find a difference of 4 points between the interventions.

The SD of 10 derived by PROMIS was ascertained based on a sample of children with a higher proportion of chronic illness than the general population. It is anticipated that the variation in outcomes in the treatment of acute medial epicondyle fractures is likely to be less than in a chronic illness. Therefore, an adaptive trial design, with blinded sample size re-estimation based on the SD of the outcome tool when patient recovery is beginning to plateau, is planned. We will perform the sample size re-estimation calculation after the first the 50 patients have completed 6 months follow-up (estimated to be month nine of the main trial). If, as expected, the standard deviation of the sample is notably less than the chronic disease population, we will revisit the study timelines to determine the optimal study duration thereby enhancing the efficiency of the trial. In the unlikely event that standard deviation is greater than expected, we will discuss the findings with the trial steering committee to formulate a strategy to meet the increased recruitment target required.

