3.3 Sample Size

Extremity Score for Children. Raw scores are translated into standardised T scores with a population mean of 50 and a Standard Deviation (SD) of 10. The 'Minimally Clinically Important Difference' (MCID) for the PROMIS Upper Extremity Score amongst children with milder forms of disability has been demonstrated to be three to

four [11], we seek to find a difference of four points. Assuming a SD of 10, a total of 266 patients (133 in each arm) is required to provide 90% power at the 5% level (two-sided) to detect a 4-point difference between the groups. Allowing for a conservative 20% loss to follow-up, we plan to recruit 334 patients in total for this trial (167 per arm).

The SD of 10 derived by PROMIS was based on a sample of children with a higher proportion of chronic illness than the general population [12], and it is anticipated that the variation in outcomes in the treatment of acute medial epicondyle fractures is likely to be less than in a chronic illness.

Independent verification of the sample size is available in

Z:\CSM_SCIENCE\Statistical Analysis\4. Sample Size**SCIENCE_SampleSize_Verification_04Apr2019.docx**, stored in the confidential statistical section of the TMF.

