6.1 Outcome Definitions

Primary Outcome PROMIS Upper Extremity: measured pre-randomised (baseline), 4 weeks (routine follow-up) and then at 6 weeks, 3 months, 6 months and 12 months via electronic collection.

The primary outcome for this study is the functional recovery assessed using the Patient Report Outcomes Measurement Information System (PROMIS Bank v2.0: Upper Limb Score for Children Computer Adaptive Test (CAT) – PROMIS is a collection of patient-reported health status tools available for children and adults that were developed to be disease non-specific in collaboration with the USA National Institute for Health [20, 21]. This is a bounded score on a standardised scale (T-score) in the interval [10 – 58] (https://www.healthmeasures.net/images/PROMIS/manuals/Scoring_Manual_Only/PROMIS_Physical_Funct ion_User_Manual_and_Scoring_Instructions_05Dec2023.pdf). These tools can be administered to healthy children, as well as to children with a variety of chronic health conditions. They are generally self-reported from the age of eight years, and proxy-reported below eight years. The PROMIS Paediatric item banks were developed using a strategic item generation methodology adopted by the PROMIS Network using item response theory. Field-testing occurred among 4,129 children aged eight to 17 years old [22]. All raw scores generated from PROMIS instruments are translated into standardized T-scores with a population mean of 50 and a standard deviation (SD) of 10. The population mean refers to the mean of the calibration sample, which, for paediatric and parent proxy instruments, is composed of a higher percentage of patients with chronic illness. Lower T scores indicate a worse outcome for upper limb function. PROMIS is available in full (30 questions), short-form (eight questions), or as a computer adaptive test 'CAT' (average eight questions). A CAT

enables the answer from one question to inform the choice of the next so that each child completing a CAT could answer a distinct set of questions to arrive at their score.

Secondary Outcomes

Sport/Performing Art Module of DASH: measured pre-randomised (baseline), 4 weeks (routine follow-up) and then at 6 weeks, 3 months, 6 months and 12 months via electronic collection.

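### The primary score is capped at 58, so a 4-point difference in underlying function could be recorded as less, and the SAP plans neither a report of scores at the cap nor an analysis that treats them as censored

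*SAP*

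**What the plan says.** **Scale.** SAP 6.1 states "This is a bounded score on a standardised scale (T-score) in the interval" 10 to 58, and describes T-scores "with a population mean of 50 and a standard deviation (SD) of 10". The sample behind that mean "is composed of a higher percentage of patients with chronic illness". Higher scores mean better function.

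**Sample size.** Protocol 7.2: "We seek to find a difference of 4 points between the interventions". It gives an MCID of 3 to 4 points and reports that families wanted 5 or more to justify surgery. SAP 3.3 uses SD 10, 90% power and a two-sided 5% level to reach 133 per arm, or 334 in total after 20% loss. Neither section mentions the upper bound. Protocol 7.2 also expects outcomes to vary less after this acute injury than in chronic disease, which means an SD below 10, but it gives no figure.

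**Ceiling evidence.** Protocol 6.3: "In the congenital limb population the PROMIS test was also the only tool without ceiling effects", with the qualification that this applied to the adaptive test and not to a short form.

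**Analysis.** SAP Table 1 names the bounded T-score as the variable and the mean difference at 12 months as the summary. SAP 6.2 fits a linear mixed model. If residual normality clearly fails, it allows a logistic transformation after rescaling by (y − min)/(max − min), and it also allows for heteroscedastic residuals. The sensitivity analyses in SAP 6.3 and 6.4 address missing data and treatment switching. No table reports how many children score the maximum, and no analysis treats those scores as censored.

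**The concern.** The cap sits close to where recovered children may score. The mean of 50 describes a group with more chronic illness. Protocol 7.1 says recovery is believed to plateau after 12 months, and the background cites a review that found excellent function without surgery. Children with congenital limb differences are a different population, so their lack of a ceiling effect says little about a healed fracture at one year.

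Where children pile up at 58, the instrument cannot separate good from better function, and the arm with better function loses more of its upper tail. The difference in mean scores is compressed, and would then be set against an MCID of 3 to 4 points and a family threshold of 5. The compression works in both directions: it shrinks a difference favouring non-operative care as much as one favouring surgery.

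One limit needs no distributional assumption. If the observed non-operative mean is above 58 − 4 = 54, a 4-point operative benefit cannot be observed; above 58 − 5 = 53, a 5-point benefit cannot. Neither document discusses this.

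**Working it through.** **1. The plan's own figure.** Per arm, n = 2(1.960 + 1.282)² × 10² / 4² = 131.4, so 132 by the normal formula. The t-based calculation gives 132.3, so 133 per arm (266 in total). Then 133/0.8 = 166.25, so 167 per arm (334). The stated figures reproduce.

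**2. Effect of the cap.**

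Inputs from the documents: cap 58, difference 4, 133 per arm, reference SD 10.

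Assumptions: latent function is normal with mean μ in the lower arm and μ + 4 in the higher arm, a common SD σ, and any value above 58 recorded as 58. The lower bound of 10 has negligible effect. I vary μ from 50 to 54 and σ from 4 to 10, because the plan expects σ below 10 but gives no value.

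With z = (58 − μ)/σ, the recorded mean is 58 − σ[zΦ(z) + φ(z)].

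For 50 v 54 with σ = 10:
- Lower arm: z = 0.8; 58 − 10(0.8 × 0.7881 + 0.2897) = 48.80; 21.2% at the cap.
- Higher arm: z = 0.4; 58 − 10(0.4 × 0.6554 + 0.3683) = 51.70; 34.5% at the cap.
- Recorded difference: 2.90.

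Recorded difference for a latent difference of 4:

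| Latent SD | 50 v 54 | 52 v 56 | 54 v 58 |
|---|---|---|---|
| 10 | 2.90 | 2.62 | 2.31 |
| 8 | 3.08 | 2.76 | 2.39 |
| 6 | 3.35 | 2.97 | 2.51 |
| 5 | 3.52 | 3.13 | 2.61 |
| 4 | 3.70 | 3.33 | 2.74 |

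The recorded difference falls below 3 once the lower latent mean exceeds about 49.2 (SD 10), 50.5 (SD 8), 51.9 (SD 6), 52.5 (SD 5) or 53.2 (SD 4).

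**3. Power.** The cap also shrinks the spread. At latent SD 10 and 50 v 54 the recorded SDs are 8.23 and 7.14, so the standard error is √((8.23² + 7.14²)/133) = 0.945. Power is Φ(2.90/0.945 − 1.96) = 86.6%. It is 84.8% at 52 v 56 and 82.5% at 54 v 58. At latent SD 8 the three values are 97.3%, 96.6% and 95.4%, and smaller SDs give more.

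**4. The logistic fallback.** The printed rescaling gives exactly 1 for a maximum score and 0 for a minimum score, and the logit is undefined at both. A small adjustment away from 0 and 1 makes it computable, but all capped children remain tied at one value. A simulation (200 replicates per scenario, 133 per arm, one visit, that adjustment added as an assumption) gave these mean estimates of a latent difference of 4:

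| Lower mean, SD | Linear | Logit, back-transformed | Tobit |
|---|---|---|---|
| 50, 10 | 2.97 | 2.24 | 4.07 |
| 52, 10 | 2.57 | 1.47 | 3.93 |
| 54, 10 | 2.34 | 1.00 | 4.06 |
| 50, 6 | 3.42 | 3.49 | 4.08 |
| 54, 6 | 2.49 | 1.38 | 3.96 |

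The data were generated from a normal latent score, which is the Tobit model's own assumption, so the last column is its best case.

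**The case against.** **The estimand is the bounded score.** SAP Table 1 defines it that way, and the linear model targets it. A reader might infer that the primary estimate is biased. It is not, for its stated target; it is compressed only relative to latent function, which the trial does not define as its target. This stands, and it makes the point one of interpretation.

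**The size is conditional.** A reader might infer that a true 4 points would be measured as under 3. The documents give no 12-month mean and expect an SD below 10. At 50 v 54, SDs of 8 to 4 give 3.08 to 3.70, all above 3. This also stands.

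**No rule reads a small difference as no benefit.** Inference is a two-sided 5% test with a 95% interval. In the 50 v 54, SD 10 case the interval would be about 2.90 ± 1.85, which excludes 0 and includes 4. So the documents do not support the inference that the trial would wrongly dismiss surgery.

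**The bound was noticed.** Table 1 calls the scale bounded. SAP 3.6 plans a blinded look at distributions, SAP 6.2 plans residual checks and a transformation, and protocol 10.1 allows non-parametric tests. None of these counts the children at the cap by arm or recovers a difference beyond it.

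**The no-ceiling sentence.** Protocol 6.3 already confines it to the congenital limb population, so it needs no edit.

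**Conclusion.** The point holds as a conditional one about interpretation. If many children score 58 at 12 months, the planned mean difference could understate a 4-point difference in underlying function, to about 2.3 to 3.7 points, and could look smaller than the MCID in either direction of effect. This rests on a normal latent score, latent lower-arm means of 50 to 54 and SDs of 4 to 10, none of which the documents supply.

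Two stronger readings are not supported. The first is that the stated 90% power fails. It is correct for a 4-point difference in scores with SD 10. For a latent 4-point shift it drops to 82–87% only at latent SD 10, and at SD 8 or less it stays above 90% over these means. The second is that a censored model should decide how the primary result is read. That model depends on the shape of the distribution above 58, which the data cannot check.

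Two gaps are unconditional: no report of the share at the maximum is planned, and the printed logit rescaling is undefined at the bounds.

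**What to change.** In SAP 6.2 and 6.4:

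1. Report the number and percentage of children at the maximum score, by arm and visit.
2. Pre-specify a sensitivity analysis of the 12-month contrast that treats maximum scores as right-censored: a mixed-effects Tobit model with the same fixed and random effects. Report it beside the unchanged primary estimate, and state that it relies on latent normality.
3. If the logistic transformation is kept, change the rescaling so that scores at either bound fall strictly between 0 and 1.

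In SAP 3.3, at most add a note. It would say that the sample size assumes no ceiling, that at latent SD 10 power for a latent 4-point shift would be about 82–87% (latent means 50 to 54), and that at SD 8 or less it stays above 90%.

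The cost is a few table rows, one supporting model and a corrected formula. No new data are needed and the primary analysis does not change. The model should be specified before the results are known, because one added after a small difference appears would carry little weight.

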In summary, this study will use the PROMIS Upper Extremity Score for Children at 1 year after randomisation as the primary outcome measure. The total number of patients required to obtain a power of 90% to detect a 4-point difference between groups for the primary outcome measure will be 266; i.e. 133 patients will be required in each treatment group. With an allowance for a conservative 20% loss to follow-up, we plan to recruit 334 patients in total. To maximise trial efficiency, we will re-estimate the sample size based on the SD of the outcome tool at 6-months follow-up of the first fifty children in the trial.

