7.3 Methodology

7.3.1 Screening and Eligibility

Patients will be eligible for this study if:

- There is radiographic evidence of a displaced medial epicondyle fracture of the Humerus, with fracture displacement determined by the surgeon as per their usual clinical practice.
- They are aged between 7 and 15 years old inclusive.

Patients will be excluded from participation in this study if:

• The injury is more than two weeks old.

- There is incarceration of the medial epicondyle fragment within the elbow joint.
- The injury is part of a complex elbow fracture (i.e. fracture extending into the joint).
- There are other fractured bones elsewhere in the body, in addition to the elbow injury.
- The elbow, if dislocated, is unable to be realigned into a satisfactory position in the emergency department.
- There is evidence that the patient and/or parent/guardian would be unable to adhere to trial procedures or complete follow-up, such as insufficient English language comprehension, developmental delay or a developmental abnormality or no access by parents to the internet.

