7.5 End of trial

The end of this trial is defined as the date all data queries have been resolved and the trial database is locked for analysis of the primary and secondary outcomes.

8. Safety Reporting

Safety reporting for each participant will begin from the first point of administration of the intervention and will end when the participant has reached their final main follow up time point, at 12 months postrandomisation. This is a low risk, pragmatic trial where both of the trial interventions are in common use. In light of this, we do not anticipate many serious adverse events (SAEs) associated with either treatment.

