8.3 Reporting Procedures for Complications

Complications (i.e. AEs and SAEs that are anticipated in the routine treatment pathway, and that we have predefined) that are foreseeable in the treatment of these fractures do not need to be reported immediately, provided they are recorded in the 'Complications' section of the Case Report Forms and/or Patient Questionnaires. For this trial, such events include the following complications (including readmission or reoperation to address them):

(a) General complications – pain, pressure areas or elbow stiffness, symptomatic instability or nonunion of the bone fragments

(b) Complications specifically related to surgery - wound infection, injury/irritation to the ulna nerve, implant irritation, screw cut-out, broken or retained metalwork and the subsequent need to remove metal pins/ screws.

9. Data Management

The data management aspects of the study are summarised here with full details described in the Data Management Plan (DMP).

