Particular note will be made of complications related to the cast (e.g. pressure areas) or surgery (e.g. pain, wound infection, injury/irritation to the ulna nerve, implant irritation, screw cut-out, broken or retained metalwork, and the subsequent need to remove metal pins/screws), including hospital admission to manage these complications. These are summarised in the Table below.

Table 10: Comparison of complications & SAEs between treatment allocations

| | Operative fixation | Non-operative treatment | | OR (95 | 5% CI) | p- value |
|--|-----------------------|----------------------------|---|--------|--------|-------------|
| | n % | n | % | Raw | Adj. | |
| Number of complications* | - | | - | - | - | - |
| Participants with complications | | | | | | |
| Wound problems (from surgery*) | | | | | | |
| Elbow stiffness | | | | | | |
| Unable to move fingers normally | | | | | | |
| Patient Reported concerns | | | | | | |
| Unable to feel fingers normally | | | | | | |
| Ulna nerve problems (little & ring | | | | | | |
| fingers) | | | | | | |
| Other | | | | | | |
| Intra-operative complications | - | | - | - | - | - |
| Participants with intra-operative | | | | | | |
| complications | | | | | | |
| Ulna nerve injury | | | | | | |
| Fragmentation of bone | | | | | | |
| Wire breakage | | | | | | |
| Anaesthesia complications | | | | | | |
| Post-operative bleeding | | | | | | |
| Screw cut-out | | | | | | |
| Other | | | | | | |
| Immobilisation complications | - | | - | - | - | - |
| Participants with immobilisation | | | | | | |
| complications | | | | | | |
| Skin complication owing to pressure | | | | | | |
| area | | | | | | |
| Discomfort | | | | | | |
| Other | | | | | | |
| Unplanned surgery/hospital | - | | - | - | - | - |
| admissions* | | | | | | |
| Participants with unplanned | | | | | | |
| surgery/hospital admissions | | | | | | |
| Fracture fixation/ revision fixation | | | | | | |
| Removal of screw(s)/wire(s) | | | | | | |
| Planned removal | | | | | | |
| Irritation | | | | | | |
| Other | | | | | | |
| Nerve exploration (isolated | | | | | | |
| procedure) Nerve exploration & screw/wire | | | | | | |
| adjustment | | | | | | |
| Nerve exploration and grafting | | | | | | |
| Debride wound/ wound infection | | | | | | |
| Microbiological confirmation of | | | | | | |
| infection | | | | | | |
| Antibiotics prescribed | | | | | | |
| Other | | | | | | |

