We will then examine any association of drop-out with important prognostic factors such as age, sex, nerve injury at presentation, BMI, diabetic status, smoking status, concomitant injuries which affect limb function, clinically significant SAEs relating to the interventions (Section 6.7), and baseline PROMIS scores as well as follow-up PROMIS scores observed before drop out. If significant associations are found with pre-drop out follow-up scores then we will fit an informative missingness model following Diggle & Kenward [39] (e.g. using xteregress and/or GLLAMM in Stata) where the longitudinal PROMIS scores will be modelled jointly with the

drop-out indicator. This analysis will be undertaken only if there is evidence of dependence of drop-out indicators on observed outcome data.

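### Nothing in the complications table keeps nerve deficits that predate treatment out of the counts, and presenting nerve status is in no baseline table

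*SAP*

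**What the plan says.** **Eligibility.** Protocol 7.3.1 lists its exclusions under "Patients will be excluded from participation in this study if". They are an injury over two weeks old, an incarcerated fragment, a complex fracture, other fractures, a dislocation that cannot be satisfactorily realigned in the emergency department, and inability to adhere or complete follow-up. A nerve deficit from the injury is not among them. Dislocated elbows that are reduced satisfactorily can enter.

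**Baseline.** SAP Table 5 covers centre and dislocation status. Table 6 covers age, gender, side, arm dominance, mechanism and sport. Table 7 covers questionnaire scores. None has a nerve row. SAP 6.3 does list "nerve injury at presentation, BMI, diabetic status, smoking status" among important prognostic factors, but only to examine drop-out.

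**Outcome.** Complications are recorded at 4 weeks, 6 weeks, 3, 6 and 12 months (SAP 6.1). The same section singles out those related to the cast or to "surgery (e.g. pain, wound infection, injury/irritation to the ulna nerve, implant irritation, screw cut-out, broken or retained metalwork". Table 10 has rows for inability to move the fingers normally, inability to feel them normally, and ulnar nerve problems, with a summary row for participants with any complication. Its columns give n and % by arm, raw and adjusted ORs and a p-value. No rule compares a symptom with the child's state before randomisation.

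**Attribution and timing.** Protocol 8.3 has a category "Complications specifically related to surgery - wound infection, injury/irritation to the ulna nerve, implant irritation" and further items. Protocol 8 states: "Safety reporting for each participant will begin from the first point of administration of the intervention".

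**Adjustment.** SAP 3.7 analyses secondary outcomes similarly to the primary, with logistic regression for binary data. The main model adjusts for dislocation status, age and gender, with centre as a random effect (SAP 6.2).

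**The concern.** The three nerve rows describe states (fingers that do not move or feel normally), not events with an onset. A child who arrives with an altered little finger and still reports it at 6 weeks satisfies the row whichever treatment was given. Without presenting nerve status, the analyst cannot separate that child from one whose symptom began after treatment.

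The complication rate is secondary objective 5 (Protocol 6.2.2), nerve injury is the first complication named in the core outcome list (Protocol 6.3), and nerve damage is a stated risk of surgery (Protocol 5.2). Symptoms that no treatment caused would raise the reported rate in both arms and, under conditions set out below, would make the OR look smaller than the contrast in treatment-caused problems.

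**Working it through.** **The plan's own figure.** The documents give no complication rate, nerve-deficit rate or expected OR. The only computed figure nearby is the primary-outcome sample size, used here for the arm size. With a 4-point difference, SD 10, two-sided 5% and 90% power, the normal formula gives 132 per arm and the t-based solution 132.3, hence 133 per arm or 266 in total (power at 133: 0.904). Dividing by 0.8, 133/0.8 = 166.25, so 167 per arm and 334 in total. The plan's figure reproduces.

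**Formula.** Let p1 and p0 be the rates of treatment-caused nerve problems (operative, non-operative), and q the share in each arm whose presenting deficit is still reported at follow-up. If the two occur independently:

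- observed rate = 1 − (1 − q)(1 − p)
- observed risk difference = (1 − q)(p1 − p0)
- OR = [a/(1 − a)] / [b/(1 − b)], with a and b the observed operative and non-operative rates.

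**Assumed p1 = 6%, p0 = 2%.** True OR = (0.06/0.94)/(0.02/0.98) = 3.13.

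| q | Operative | Non-operative | OR | Risk difference |
|---|---|---|---|---|
| 0 | 6.0% | 2.0% | 3.13 | 4.0 points |
| 2% | 7.9% | 4.0% | 2.07 | 3.9 |
| 5% | 10.7% | 6.9% | 1.62 | 3.8 |
| 10% | 15.4% | 11.8% | 1.36 | 3.6 |

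**Other assumed rates**

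| New-onset rates | True OR | q = 2% | q = 5% | q = 10% |
|---|---|---|---|---|
| 5% v 2% | 2.58 | 1.80 | 1.46 | 1.27 |
| 8% v 2% | 4.26 | 2.65 | 1.95 | 1.55 |
| 10% v 5% | 2.11 | 1.81 | 1.57 | 1.38 |
| 5% v 5% | 1.00 | 1.00 | 1.00 | 1.00 |

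For 8% v 2% with 167 per arm and no losses, power is 71% if only new deficits count, and 56%, 42% and 29% at q = 2%, 5% and 10%.

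**Where the direction can fail**

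- *Chance imbalance.* The SD of the between-arm difference in presenting deficits is √(2q(1 − q)/167), which is 1.5, 2.4 and 3.3 points for q = 2%, 5% and 10%. In simulation with true rates of 8% v 2%, imbalance moved the expected OR away from 1 in about 9%, 1% and under 0.1% of draws.
- *Unequal persistence.* At q = 5% and 8% v 2%, halving persistence in the operative arm changes the OR from 1.95 to 1.55; halving it in the non-operative arm gives 3.10. At the extreme, with full persistence in the operative arm and none in the other, the OR is (0.126/0.874)/(0.02/0.98) = 7.06, above the true 4.26.

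**Rows that can be affected.** These are the three nerve-symptom rows and the participants-with-complications row. The intra-operative block (which has its own ulnar nerve injury row) and the immobilisation block concern events that cannot predate treatment.

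**The case against.** **The text can be read as excluding these deficits.** Safety reporting starts at the intervention, the complications in Protocol 8.3 are those anticipated in the treatment pathway, and a parent's report triggers a check that the site has completed a complication form (Protocol 7.1). This stands in part. The forms are not in the documents, so a reader who infers that such deficits *are* counted goes too far; what can be said is that no stated rule stops it. A reporting start date does not remove a deficit that was present on arrival and is still present at 4 or 6 weeks.

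**Nerve status may be collected.** The pre-randomisation row of Protocol Table 1 also omits side, mechanism and dislocation status, which are clearly recorded, so absence there proves nothing. SAP 6.3 plans to use nerve injury at presentation, SAP 5.3 promises comparison on other important prognostic factors, and the shell tables are to be reviewed before the final analysis (SAP 1). Non-collection is therefore not established. Equally, BMI, diabetic status and smoking status stand in the same SAP 6.3 list and are also missing from Tables 5 to 7, so the list does not establish collection. Neither place applies the item to Table 10.

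**A presenting deficit would not be booked as surgical.** A reader might infer this from Protocol 8.3. The documents do not support it. The label belongs to a list of events exempt from immediate reporting, and Table 10 puts the symptom rows in a general block shared by both arms.

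**All nerve symptoms by randomised arm is a legitimate treatment-policy outcome.** This stands. A new-or-worse count alone would miss any effect of treatment on recovery of an existing deficit, and notes may record nerve examinations more fully in operated children.

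**Conclusion.** The gap is real but limited. Such children can enter, presenting nerve status is in no baseline table, and Table 10 has nothing to keep a prior deficit out of its nerve rows or its summary row. If such deficits are reported, the complication rate is inflated in both arms.

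Dilution of the OR is conditional. It needs a true OR other than 1 and similar frequency and persistence of presenting deficits in the two arms, and it holds on average. With no true difference there is no bias. A reader might infer that a real excess would be hidden, but the risk difference shrinks only by the factor (1 − q), and Table 10 shows n and % by arm, so the absolute excess stays visible. What weakens is the relative measure and the power of its test.

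The size cannot be derived from the documents: the fall from 3.13 to 2.07, 1.62 or 1.36 rests wholly on assumed rates. The primary outcome and the intra-operative and immobilisation rows are not affected. This is a cheap improvement to one secondary outcome.

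**What to change.** 1. Add nerve status at presentation (yes, no, unknown) to SAP Table 6, taken only from records made before randomisation, including for children already enrolled. If the field exists for the drop-out analysis, only the table row is needed.
2. Keep the present nerve-symptom rows in Table 10, by randomised arm. Add rows that count only symptoms new or worse than before randomisation, and show pre-existing deficits separately.
3. Report risk differences with 95% confidence intervals alongside the ORs.

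Eligibility and treatment stay as they are.

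The cost is one baseline field from routine notes and one counting rule. Some children will be unknown, and documentation may differ by arm, so report unknowns by arm and read the new-or-worse count beside the all-symptom count, not in place of it.
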